6.1 Informed Consent/Assent and HIPAA Authorization	
6.2 Screening Process	
6.3 Study Interventions and Follow-Up	
6.4 Description of Study Procedures/Evaluations	
6.5 Study Team Training and Intervention Reliability	
6.6 Concomitant Interventions and Procedures	
Section 7 SAFETY ASSESSMENTS AND REPORTING	15
Section 8 STATISTICAL CONSIDERATIONS AND ANALYSIS	16

	8.1	Statistical and Analytical Plans (SAPs)	
	8.2	Statistical Hypotheses	
	8.3	Analysis Datasets	
	8.4	Description of Statistical Methods	
	8.5	Sample Size	
	8.6	Measures of Minimize Bias	
Section 9		DATA QUALITY AND OVERSIGHT	18
	9.1	Study Team Quality Assurance and Quality Control	
	9.2	Data Safety and Monitoring Plan	
Section 10		ETHICAL CONSIDERATIONS	19
	10.1	Ethical Standard	
	10.2	Institutional Review Board (IRB)	
	10.3	Maintaining Subject Privacy	
	10.4	Maintaining Study Data Confidentiality	
	10.5	Study Support and Conflicts of Interest	
Section 11		DATA HANDLING AND RECORD KEEPING	20
	11.1	Data Management Responsibilities	
	11.2	Data Capture Methods	
	11.3	Study Record Retention Policy	
Section 12		PUBLICATION POLICY	21
Section 13		REFERENCES	21

Protocol Revision History

Protocol Version with Summary of Changes	Version Date
Initial Submission v1	08/27/2025
Revision v2	11/20/2025
Revision v3	11/21/2025
Revision v4	11/24/2025
Revision v5 (for ClinicalTrials.gov to remove personal pronouns)	02/04/2026
Revision v6 (for ClinicalTrials.gov to remove personal pronouns)	02/11/2026

List of Abbreviations

ACGME	Accreditation Council for Graduate Medical Education
DSMB	Data Safety Monitoring Board
GME	Graduate Medical Education
HIPAA	Health Insurance Portability and Accountability Act
IRB	Institutional Review Board
OHRP	Office for Human Research Protections
PI	Principal Investigator
RE	Reportable Event

Protocol Summary

Title:	Creating a Flexible Curriculum Tool for Pediatric Palliative Care Rotating Learners
Brief Summary:	The overall objective of this study is to determine if a flexible curriculum tool can improve the experience of rotators with the pediatric palliative care team, measured by their perception that the rotation helped achieve standard and their personal learning objectives. This is a pilot study that will compare rotation evaluations before and after implementing a flexible curriculum tool that uses a database of resources to supplement the clinical rotation education and tailor it to the needs of each learner.
Study Population:	The target population will be a convenience sample of trainees rotating with the palliative care team. This will include physicians in training (hospice and palliative medicine fellows, pediatric subspecialty fellows, pediatric and other residents, medical students), NP students, pharmacy residents, allied health professional students and fellows, research associates, and any other learner who does clinical shadowing. The investigators expect to have about 30 learners over the course of the year, based on 29 last year.
Study Site(s):	Children's National Hospital
Number of Participants:	The investigators anticipate a maximum of 30 participants – 15 for the control group and 15 for the intervention group
Accrual Ceiling:	40 participants
Study Duration:	24 months
Subject Duration:	2-7 months (depending on timing of their rotation compared to the focus group)
Objective(s):	Primary: To evaluate if use of a flexible education tool using a palliative care education database is more effective than standard educational practices in meeting standard learning objectives.

Methodology:
	
Secondary: To evaluate if use of a flexible education tool using a palliative care education database is more effective than standard educational practices in meeting learner-specific rotation objectives.
 
Unblinded pilot medical education study with convenience sampling and control group to compare to intervention group

Outcome Measures:
	
Primary: response to the question “I achieved the standard objectives of the rotation (which will be provided to the learner).” It will be quantified using a Likert scale with five choices, 1-5, with 1 set to strongly disagree and 5 set to strongly agree.
 
Secondary: response to the question “I achieved my specific objectives for the rotation (which the learner provided at the start of the rotation).” It will be quantified using a Likert scale with five choices, 1-5, with 1 set to strongly disagree and 5 set to strongly agree.


Study Intervention/Procedures:
 
Statistical Analysis:
	
This is a single center, unblinded pilot study evaluating the use of a flexible curriculum tool to improve the experience of rotators with the palliative care team, measured by how well the rotation helps them meet standard as well as individualized learning objectives. All learners in the first half of the study period will be in the control group and all learners in the second half of the study period will be in the intervention group. Outcomes will be measured on post-rotation evaluation surveys, sent to each trainee after their rotation is complete. Qualitative data will be further interrogated with a focus group of trainees in the intervention group.
 
Demographic data will be reported using descriptive statistics. A Mann-Whitney U test will be used to compare distribution of responses to Likert scale questions between control and intervention groups and inductive thematic analysis to analyze responses to open-ended survey questions and focus group transcriptions.

Section 1: Key Roles

Principal Investigator	Co-Principal Investigator
[name]/MA	[name]/PhD
Palliative Care Attending Physician, Hospice and Palliative Medicine Fellowship Program Director	Palliative Care Attending Physician, Hospice and Palliative Medicine Fellowship Associate Program Director
Children's National Hospital	Children's National Hospital
[name]	[name]
[contact]	[contact]
[contact]	[contact]

There are no study leadership committees. The principal investigator will provide oversight of the data. The investigators do not expect to have many adverse or unexpected events (see more in detail below), but they will respond to any complaints or adverse or unexpected events as required by the Children's National OPHS policy on reportable events.

Section 2: Introduction, Background Information and Scientific Rationale

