2.2 Scientific Rationale

The pediatric palliative care team at Children's National Hospital supports learners at various levels, with different experiences and goals during their clinical rotations. Some seek to learn about primary palliative care skills, to learn about palliative care careers, or to develop expertise in pediatric palliative care. The team attempts to tailor educational experiences to standard and individualized learning goals and timeframes on service (half day to a few months). It would be helpful to have a database of resources to support these learners for the time on rotation and afterwards. There are multiple databases that exist to serve as tools for medical education, including PubMed, Cochrane Central, MedEdPORTAL, Embase, and ERIC. They provide access to primary literature and books, supporting evidence-based practice, but do not include podcasts, modules, videos, and lectures that are powerful educational tools. Palliative care clinicians utilize *ad hoc* methods to meet learner goals by providing literature that compliments patient encounters or learner inquiries. Tailoring education to meet individualized learning goals at the appropriate level for the learner and the length of their rotation takes energy and time to execute, so it is difficult to do well.

The purpose of this pilot project is to use the Framework for Flexible Education¹⁰ to develop and evaluate a flexible curriculum tool that permits quick connections to resources for educators and learners that are stored in a bespoke and updatable database. The investigators would like to assess if it improves 1) meeting standard objectives and "elective objectives" and 2) the experience of trainees during their rotation. The hypothesis is that it will improve the ability of the rotation to meet learners' objectives as measured by Likert-scale-based end of rotation evaluations as well as open-ended questions and a focus group.

The study population is a convenience sample of learners who choose to rotate with the palliative care team. The control condition was chosen to be approximately half of the academic year with the intervention the other half. The palliative care team does not have rotators (outside of the pediatric palliative care fellow) during July, so that month was excluded. This pilot study will be performed over the course of the academic year in order to facilitate the teaching team's ability to improve education for the next year of learners.

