5.1 Study Population, Recruitment and Retention

- Target sample size: This will be a convenience sample of learners already scheduled to rotate with the palliative care team. There is an anticipated approximately 20 learners per group screened and hope to recruit about 15 per group
- Anticipated accrual rate: 60-75%
- Training site: Children's National Hospital
- Recruitment site: only those who rotate with the palliative care team at Children's National Hospital
- Restrictions to enrollment: none

- Participation will not be limited based on health, only that they need to be healthy enough to participate in the palliative care rotation for at least ½ day, as the target population is trainees
- Participants will be incentivized to participate in the focus group with a \$20 gift card to a location approved by the IRB to compensate them for their time

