8.5 Sample Size

Because this is a pilot study to improve the education of an existing population on a rotation with a small team, the sample will be a convenience sample of learners who rotate with the palliative care team. It is expected that there will be approximately 20 learners to recruit and screen for each (control and intervention) group and to enroll at least 10 and up to 15 for each group. It is accepted that the statistical analysis may be underpowered, which is why the pilot study will be supplemented with qualitative data.

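### The Protocol Summary expects about 30 learners in the year, but sections 5.1 and 8.5 plan on about 40, so the hoped-for 15 per group does not follow from the documented pool

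*Protocol*

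**What the plan says.** The Protocol Summary (Study Population) gives the size of the pool and where it comes from: "The investigators expect to have about 30 learners over the course of the year, based on 29 last year". Under Number of Participants it adds: "The investigators anticipate a maximum of 30 participants", split 15 and 15, with a separate accrual ceiling of 40.

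Section 5.1 anticipates "approximately 20 learners per group screened and hope to recruit about 15 per group" and gives "Anticipated accrual rate: 60-75" per cent. Section 8.5 repeats "approximately 20 learners to recruit and screen for each (control and intervention) group" and expects "to enroll at least 10 and up to 15 for each group".

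The two groups fill one 12-month window. Section 2.2 says: "The control condition was chosen to be approximately half of the academic year with the intervention the other half". Section 6.3 sets January to June 2026 for control and July to December 2026 for intervention, and section 8.4 describes two six-month periods with no learner in both. Recruitment is confined to rotators (5.1), there are no exclusion criteria (5.3), and all eligible rotators are sent the evaluation (6.2).

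**The concern.** The people who can be screened are the people who rotate. The protocol puts that number at about 30 in one place and about 40 in two others, for the same length of time. Only the figure of 30 has a stated source, the previous year's count of 29.

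The enrolment figures depend on which pool is used. The protocol has no power calculation, so the forecast of available learners is the only quantitative support for the sample size in 8.5. If the pool is about 30, readers and the IRB are shown a screened number and a hoped-for enrolment that the rotation would not be expected to supply.

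**Working it through.** **Inputs**
- Pool: about 30 learners a year, 29 the year before (Protocol Summary).
- Screened: about 20 per group (5.1, 8.5).
- Accrual: 60-75% (5.1).
- Enrolment: about 15 per group hoped for (5.1); 10 to 15 per group expected (8.5).
- Accrual window: 6 + 6 = 12 months, no learner in both groups (6.3, 8.4).

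**Formula:** expected enrolment = learners available × accrual rate.

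**1. The plan's own figure.** 20 × 0.75 = 15 and 20 × 0.60 = 12. The hoped-for 15 per group is reproduced at the top of the accrual range, and only with 20 per group.

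**2. The two pools.** 2 × 20 = 40 distinct learners. 40/30 = 1.33 and 40/29 = 1.38, so sections 5.1 and 8.5 assume 33% more learners than the Summary expects and 38% more than were seen last year.

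**3. Expected enrolment from each pool**

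| Pool | Total at 60% | Total at 75% | Per group, even split |
|---|---|---|---|
| 40 | 24 | 30 | 12 to 15 |
| 30 | 18 | 22.5 | 9 to 11.25 |
| 29 | 17.4 | 21.75 | 8.7 to 10.9 |

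The totals need no assumption about how learners divide between the half-years. The per-group column assumes equal halves, because the protocol gives no half-year counts.

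**4. Participation needed for the stated enrolment**
- Two groups of 15: 30/40 = 75%, but 30/30 = 100%. From 29 learners it is 30/29 = 103%, which is impossible.
- Two groups of 10: 20/40 = 50%, but 20/30 = 67% and 20/29 = 69%.

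With 40 learners, 10 per group lies below the accrual range and leaves a margin. With 30, it lies inside the range: at 60% the expected number is 9 per group, at 75% it is 11.25.

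**5. Expected versus realised numbers.** With 15 learners available, each taking part independently with probability 0.60 (a binomial assumption), the chance that a group reaches 10 or more is about 40%. For both groups it is about 0.40 × 0.40 = 16%. So 10 per group can be reached even at the bottom of the accrual range, but it is not assured.

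**The case against.** **Could the figures be reconciled?** The 30 cannot mean enrolled participants, because it rests on a count from the year before the study. The accrual ceiling of 40 is a cap and not a forecast. The 24-month study duration adds no learners, because each group accrues for six months. The year behind the 30 is not defined as calendar or academic, but either is 12 months. The wording is hedged throughout, yet 10 in 30 is more than rounding.

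**Does it matter?** The protocol concedes: "It is accepted that the statistical analysis may be underpowered". Everyone eligible is invited whatever the forecast, no analysis set or decision rule is tied to the number enrolled, and qualitative data supplement the comparison. This stands, and it limits the weight of the point.

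Stronger readings that a reader might infer, and that the documents do not support:
- *The Summary contradicts itself.* A maximum of 30 participants from about 30 learners is coherent, and the upper figure of 15 in 8.5 is likewise a bound. Only 5.1 treats 15 per group as something to aim for.
- *Ten per group is out of reach, or reachable only at high accrual.* That confuses expected with realised enrolment (step 5). Ten also lies within the 9 to 11 expected from 15 learners, so the figure need not be dropped.
- *All the enrolment figures were built on 40.* Fifteen fits 40. Ten is 50% of 20, below the stated accrual range, and fits that range only with a pool of about 30.
- *The intervention group will be the smaller one because July is nearly empty.* Section 2.2 says July was excluded, while 6.3 starts the intervention period in July. Sizing the effect would require even flow over the other months, and no monthly counts are given.

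**Conclusion.** The inconsistency is real: about 30 learners in the Summary against about 40 in 5.1 and 8.5, for the same 12 months. On the documented pool and the stated accrual, expected enrolment is 18 to 22.5 in total and not 24 to 30. The hoped-for 15 per group does not follow from that pool, and 10 per group is about what should be expected, not a minimum that can be relied on.

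The totals assume that the yearly figure of about 30 applies to January to December 2026 and that the accrual rate applies to all rotators. The per-group range of about 9 to 11 also assumes equal halves. The point should be fixed, but its practical weight is modest: no power statement is invalidated and no analysis changes.

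**What to change.** Use one pool figure in the Summary, 5.1 and 8.5, in one of two ways:
- Keep about 30 learners. Restate the screened number as about 15 per group and expected enrolment as about 9 to 11 per group, say that this assumes equal halves, and present 10 as an expectation and 15 only as a maximum.
- Keep about 20 per group. State why 40 learners are expected after 29 last year, and correct the 30 in the Summary. The present enrolment figures can then stay.

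As a separate minor point, reconcile the exclusion of July in 2.2 with the July start of the intervention period in 6.3.

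The cost is a wording amendment and, under the first option, a less favourable stated sample size. No procedure or analysis changes. Reconciling July may change a stated date.

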2.1 Background Information and Relevant Literature

It estimated that 2017, more than 21 million children worldwide would have benefited from pediatric palliative care services, and over 8 million would benefit from pediatric palliative care services delivered by a specialist.¹ Palliative care is accepted as a part of standard of care for children with severe illnesses,² but this need is not being met, partially because of a lack of educational opportunities.³

To that end, there have been many educational interventions developed for education of trainees^{4,5} as well as pediatric specialists in principles of palliative care.⁶ While there are developed standards of education for pediatric palliative care education, by the Accreditation Council for Graduate Medical Education (ACGME) in the United States, as well as by other groups in the United Kingdom,⁷ many learners also have individual goals uniquely suited to their practice needs, especially if they do not primarily practice pediatric palliative medicine.⁸

Some educators in pediatric palliative care have utilized more tailored interventions for learners, but they target balancing the patient versus trainee experience,⁹ not necessarily aligning the trainee experience with their

individualized learning goals, especially within the limitations of clinical rotations in a busy training program.

2.2 Scientific Rationale

The pediatric palliative care team at Children's National Hospital supports learners at various levels, with different experiences and goals during their clinical rotations. Some seek to learn about primary palliative care skills, to learn about palliative care careers, or to develop expertise in pediatric palliative care. The team attempts to tailor educational experiences to standard and individualized learning goals and timeframes on service (half day to a few months). It would be helpful to have a database of resources to support these learners for the time on rotation and afterwards. There are multiple databases that exist to serve as tools for medical education, including PubMed, Cochrane Central, MedEdPORTAL, Embase, and ERIC. They provide access to primary literature and books, supporting evidence-based practice, but do not include podcasts, modules, videos, and lectures that are powerful educational tools. Palliative care clinicians utilize *ad hoc* methods to meet learner goals by providing literature that compliments patient encounters or learner inquiries. Tailoring education to meet individualized learning goals at the appropriate level for the learner and the length of their rotation takes energy and time to execute, so it is difficult to do well.

The purpose of this pilot project is to use the Framework for Flexible Education¹⁰ to develop and evaluate a flexible curriculum tool that permits quick connections to resources for educators and learners that are stored in a bespoke and updatable database. The investigators would like to assess if it improves 1) meeting standard objectives and "elective objectives" and 2) the experience of trainees during their rotation. The hypothesis is that it will improve the ability of the rotation to meet learners' objectives as measured by Likert-scale-based end of rotation evaluations as well as open-ended questions and a focus group.

The study population is a convenience sample of learners who choose to rotate with the palliative care team. The control condition was chosen to be approximately half of the academic year with the intervention the other half. The palliative care team does not have rotators (outside of the pediatric palliative care fellow) during July, so that month was excluded. This pilot study will be performed over the course of the academic year in order to facilitate the teaching team's ability to improve education for the next year of learners.

2.3 Potential Risks

Minimal risk to subjects is expected. Survey data will be de-identified. Expected time commitment for survey participants is 5 minutes for survey completion, in addition to possible participation in the focus group. For those who participate in the focus group, there is a risk that information shared in the group will not be kept private by other participants.

2.4 Potential Benefits

There is minimal likelihood of direct benefit to subjects, as they would benefit from the educational intervention whether they participate in the study. Indirect benefits may include laying groundwork for future improvement of palliative care education.

Section 3: Objectives and Endpoints

The overall objective of this study is to determine if a flexible curriculum tool can improve the experience of rotators with the pediatric palliative care team, measured by their perception that the rotation helped achieve standard and personal learning objectives. The hypothesis is that the rotators who rotate when the tool is in use will be more likely to agree or strongly agree that learning objectives will be met.

3.1 Primary Objective(s)

To evaluate if use of a flexible education tool using a palliative care education database is more effective than standard educational practices on the pediatric palliative care team in meeting standard rotation learning objectives.

3.2 Secondary Objective(s)

To evaluate if use of a flexible education tool using a palliative care education database is more effective than standard educational practices on the pediatric palliative care team in meeting learner-specific rotation objectives.

3.3 Primary Outcome Measure(s)

The primary outcome measure is response to the question “I achieved the standard objectives of the rotation (which will be provided to the learner).” It will be quantified using a Likert scale with five choices, 1-5, with 1 set to strongly disagree and 5 set to strongly agree.

3.4 Secondary Outcome Measure(s)

The secondary outcome measure is response to the question “I achieved my specific objectives for the rotation (which the learner provided at the start of the rotation).” It will be quantified using a Likert scale with five choices, 1-5, with 1 set to strongly disagree and 5 set to strongly agree.

Other outcome measures include whether (via Likert scale, scores ranging from Strongly Disagree to Strongly Agree as defined above):

- The learner was provided with a variety of resources to meet their learning objectives
- The education they received matched their level of training
- Their education was appropriate to their previous exposure to hospice and palliative medicine
- The education matched their learning style
- They felt the rotation was valuable

- The clinical educators promoted an open, respectful, and safe environment for discussion, learning, and improvement
- They would recommend this rotation to others

Open-ended feedback will be elicited regarding strengths of the rotation, areas for improvement, and practice changes, both on the survey and during the focus group.

Lastly, learners will be assessed on their confidence in meeting each standard rotation objective, on a Likert scale of 1-5, both before and after the rotation.

All of this allows the team to gather more information to understand why there was benefit for the flexible learning curriculum, if indeed there was one.

Section 4: Study Design

This is a single-center pilot study evaluating the use of a flexible curriculum tool to improve the experience of rotators with the palliative care team, measured by how well the rotation helps them meet standard as well as individualized learning objectives. It will not be blinded.

All learners will be sent a welcome email that will include a pre-rotation self-assessment, identifying type of learner and personal experience with palliative care, self-identified preferred ways of learning, length of time on the rotation, and personal learning goals.

All learners in the first half of the study period will be in the control group, and all learners in the second half of the study period will be in the intervention group. Outcomes will be measured on post-rotation evaluation surveys, one for each trainee, sent to them after their rotation is complete. Qualitative data will be more deeply interrogated with a focus group of trainees who participated in the intervention.

Section 5: Study Enrollment and Withdrawal

